5.1.5 Subject Disposition

The disposition of all subjects with respect to Extension A and B will be summarized for all enrolled subjects. Subject disposition summaries will present the number (percentage [%]) of subjects who had discontinued or completed, and the primary reason for discontinuation.

5.1.6 Protocol Deviations

Not applicable.

5.1.7 Demographic and Other Baseline Characteristics

Demographic and other baseline characteristics for the Safety Analysis Set (Extension) will be summarized.

Continuous demographic and baseline variables include age, weight, height and body mass index (BMI); categorical variables include sex, age group (2-<12, 12-<18, 18-<65, ≥65), race and ethnicity.

Age is recorded at date of informed consent.

MEDICAL HISTORY

Epilepsy-specific medical history, including time since diagnosis and seizure type will be summarized for the Safety Analysis Set (Extension) using descriptive statistics.

5.1.8 Prior and Concomitant Therapy

The number of baseline AEDs will be summarized and a summary of baseline AEDs will be produced. A baseline AED is an AED taken at the date of randomization to the Core Study.

Other Prior and Concomitant Therapy will be listed.

5.1.9 Treatment Compliance

Investigator assessment of compliance, as recorded on the e-CRF at each visit, will be listed.

5.2 DATA ANALYSIS GENERAL CONSIDERATIONS

5.2.1 Pooling of Centers

There will be no pooling of centers.

5.2.2 Adjustments for Covariates

No models will be fitted to the data hence there will be no adjustments for covariates.

5.2.3 Multiple Comparisons/Multiplicity

As no P-values will be reported, there will be no multiplicity issues.

5.2.4 Examination of Subgroups

All summaries will be presented by the following age groups and overall: 2-<12years, 12-<18 years, 18-<65 and 65 years and above.

5.2.5 Handling of Missing Data, Drop-outs, and Outliers

A conservative principle will be used for an AE with missing date(s) to determine if it is treatment-emergent, that is, if there are missing or partially missing AE start and/or stop dates, and it cannot be determined definitively whether an AE started during the perampanel treatment duration, it will be assumed that the AE was treatment-emergent.

If the day and month are missing, events will be considered treatment-emergent if the year is equal to or after the year of the first dose date; if days are missing, events will be considered treatment-emergent if the year is after the year of the first dose, or if the year is equal to the year of the first dose date and the month is equal to or after the month of the first dose date. A similar principle will be used for a medication with missing date(s). If there are missing or partially missing medication start and/or stop dates, and it cannot be determined definitely whether a medication was taken concomitantly with perampanel, it will be assumed that the medication is concomitant. A detailed algorithm to impute missing dates is given in the programming specifications.

For the purpose of summarizing maximum severity, if the severity of an adverse event (AE) is missing for a subject, then, if this subject has another AE with the same preferred term that has “severe” severity, the maximum severity of the AE will be noted as “severe”; otherwise the maximum severity will be noted as missing. Similarly, for the purpose of summarizing closest relationship, if the relationship of an AE to study drug is missing, the AE will be noted to be probably related if there is another probably related AE with the same preferred term, otherwise this relationship will be noted as missing.

No special handling of missing data is planned for the analysis of any of the other safety variables.

All the listings will display the original missing values.

5.2.6 Other Considerations

A subject who has an AE coded to the same preferred term more than once during perampanel treatment will be counted only once in calculations for that AE. Similarly, if a subject has more than one AE in a system organ class (SOC), the incidence will be counted only once for that SOC. If a subject has the same AE more than once, the occurrence that is of greatest severity will be used in the calculation of the incidence of individual AE by severity. Similarly, the AE considered most closely related to open-label treatment will be used in the calculation of incidence of individual AE by relationship.

If no seizure diary data is observed during a period, then the seizure frequency per 28 days for that period will be set to missing. Missing diary data should not be interpreted as equivalent to a non-missing record of zero.

5.3 EFFICACY ANALYSES

Seizure frequency for a given seizure type (or overall) for any given interval will be based on the number of seizures of that particular type (or overall) recorded over the given interval based only on “days with a valid seizure count,” and rescaled to a 28-day window, calculated as the number of seizures over the time interval, multiplied by 28, and divided by the number of “days with a valid seizure count” in the interval. A “valid day” is defined as the day where seizure counts information is present, that is, either a record with an answer of ‘No’ to the question ‘Did the subject experience any seizures?’ or a positive number of seizures for at least one of the seizure types collected. “Valid seizure counts” are the seizure counts that are read from the valid seizure days.

The baseline for a given seizure type (or total) is defined as the seizure frequency per 28 days of the given type (or total) based on all valid seizure diary data dated before the first dose date of perampanel. Although driven by first dose date and not time periods, this means that for subjects randomized to perampanel in the Core Study, baseline will be based on all valid seizure diary data occurring during the Core Study baseline period whereas baseline for subject randomized to placebo in the Core Study will be based on all valid seizure diary data from the Core Study prior to the first dose in the Extension Phase.

The perampanel treatment duration for efficacy analyses consists of (a) the Randomization Phase of the Core Study plus the Extension Phase A for subjects randomized to the perampanel treatment arm during the Core Study, or (b) the Extension Phase A for subjects randomized to placebo treatment during the Core Study.

5.3.1 Pre-Perampanel Baseline Analysis

The following analyses will be conducted for drop, non-drop and total seizures using the Full Analysis Set (Extension):

- Median percentage change in seizure frequency per 28 days from baseline over the entire perampanel treatment duration.

- Proportion of subjects with $\geq 50\%$, $\geq 75\%$, and 100% response for the perampanel treatment duration.

Efficacy endpoints will be summarised in 13-week intervals and overall.

For summaries by 13-week intervals a subject needs at least 1 day of seizure frequency data in a 13-week interval to be included in the summary for the overall perampanel treatment duration. To be counted as seizure-free, they would need to have completed the time interval.

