9.1.3 Extension A

A subject who completes the Maintenance Period of the Core Study will be eligible to enter Extension A, which consists of 3 periods: Conversion Period (6 weeks), Maintenance Period (46 weeks), and Follow-up (4 weeks; only for those subjects not entering into Extension B). The total treatment duration in Extension A is 52 weeks for evaluation of long term safety and efficacy. (revised per Amendment 04)

Subjects will immediately begin the blinded Conversion Period starting at Week 19. During the Conversion Period, subjects who received perampanel during the Core Study will continue receiving perampanel in a blinded manner at the same dose received during the Core Maintenance Period. Subjects who received placebo during the Core Study will begin treatment with perampanel in a blinded manner, following the same dosing regimen and titration schedule as that in the Core Study, starting at 2 mg/day and will then be up-titrated as described above for the Core Study, to the optimal dose per the investigator's discretion, not to exceed a maximum dose of 8 mg/day. After the double-blind Conversion Period, subjects can be titrated up to 12 mg/day (except in Japan, where the maximum allowed dose remains at 8 mg/day), in 2-week intervals during the Extension A Maintenance Period as per the investigator's discretion. The total treatment duration in Extension A is 52 weeks for evaluation of long term safety and efficacy. Addition, deletion, and dose changes to the concomitant AEDs are allowed during Extension Maintenance Period. (revised per Amendment 04)

After completion of Extension A, an additional Extension Phase (Extension B) with open-label treatment will be available for optional participation to subjects who reside in Japan or subjects in countries where an extended access program (EAP) cannot be implemented or has not yet been implemented, and who in the opinion of the investigator continue to benefit from treatment with perampanel. All subjects, except for those entering Extension B, will enter a 4-week Follow-up Period, which will have 1 visit during which End-of-Study assessments will be performed. (revised per Amendment 04)

Further information regarding Extension A is provided in [Appendix 2](#).

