7 CHANGES IN THE PLANNED ANALYSES

Limited data summaries are being produced due to the early termination of the study. Any future changes to the analysis will be documented separately and will be addressed in the Clinical Study Report.

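### Extension 13-week summaries: one diary day is enough to be scored for 50%/75% response, while seizure freedom needs a completed interval, which the schedule rules out in interval 6

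*SAP*

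**What the plan says.** Extension SAP 5.3.1 plans percent change and the proportions with at least 50%, at least 75% "and 100% response for the perampanel treatment duration". It adds: "Efficacy endpoints will be summarised in 13-week intervals and overall". Two rules follow.

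- **Inclusion:** "a subject needs at least 1 day of seizure frequency data in a 13-week interval to be included in the summary". The same sentence opens with the 13-week summaries but finishes "to be included in the summary for the overall perampanel treatment duration", so it is not clear whether it governs each interval or the overall summary.
- **Seizure freedom:** "To be counted as seizure-free, they would need to have completed the time interval". The SAP does not define completion, and does not say whether this rule also governs 100% response.

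Under Extension SAP 5.3 the frequency is "rescaled to a 28-day window, calculated as the number of seizures over the time interval, multiplied by 28" and divided by the valid diary days in the interval, with no minimum. Section 5.2.6 makes it missing only when the period has no diary data at all.

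On duration, Protocol 9.1.3 states: "The total treatment duration in Extension A is 52 weeks for evaluation of long term safety and efficacy". Extension SAP 5.3 adds the Core Randomization Phase for subjects randomised to perampanel. Extension SAP 7 records: "Limited data summaries are being produced due to the early termination of the study".

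**The concern.** The two rules treat a short interval differently. A subject with one seizure-free diary day in an interval scores as a 50% and a 75% responder. The same subject stays in the denominator for seizure freedom but cannot enter the numerator. Short intervals are to be expected: the 13-week grid does not fit the planned 70 weeks, the last visit has a window, the study stopped early, and Protocol Appendix 2 lets Extension A end sooner if commercial supply or an access programme starts.

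The 13-week intervals are the only time-resolved efficacy display in the Extension SAP, so they will be read as evidence on whether the effect lasts. Section 5.2.4 also splits every summary into four age groups, so a few very short intervals can move a small cell.

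**Working it through.** The plan states no figure behind these rules, so there is nothing to reproduce. The check has five steps.

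**1. Schedule.** Inputs: Core 6 + 12 weeks (Protocol 9.1), Extension A 52 weeks (9.1.3), interval 13 × 7 = 91 days, Visit 14 window ±6 days (Protocol Table 8).
- Perampanel-randomised: (18 + 52) × 7 = 490 = 5 × 91 + 35. Interval 6 has 35 planned days, and 35 + 6 = 41 with the latest in-window visit. Neither reaches 91.
- Placebo switchers: 52 × 7 = 364 = 4 × 91. A visit 1 to 6 days late opens a fifth interval of 1 to 6 days. A visit 6 days early leaves interval 4 at 91 − 6 = 85 days, and the SAP does not say whether that is complete.

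**2. Exact Poisson at the entry minimum, no effect.** Protocol 9.1.1.2 requires 2 drop seizures per week, B = 8 per 28 days. Treat B as known. With D valid days the expected count is B × D/28, and a subject is a 50% responder if the count is at most half of that.
- D = 1: expected 0.286, so only a zero count qualifies. P = exp(−0.286) = 75.1%, for both 50% and 75% response.
- D = 35: expected 10. P(X ≤ 5) = 6.7%; for 75% response, P(X ≤ 2) = 0.3%.
- D = 91: expected 26. P(X ≤ 13) = 0.4%; for 75% response, about 0%.

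**3. Higher rates, no effect (simulation).** Assumed: a 28-day baseline with at least 8 seizures, Poisson counts, weekly CV 0 to 0.5. Chance of scoring as a 50% responder:

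| Seizures per 28 days | 1 day | 35 days | 91 days |
|---|---|---|---|
| 10 | 70-71% | 7-15% | 2-7% |
| 20 | 49-52% | 1.3-6.7% | 0.2-2.5% |
| 40 | not tabulated | 0.1-4.2% | 0-1.3% |
| 80 | not tabulated | 0-2.9% | 0-0.8% |

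At 20 per 28 days the chance is 27-32% on 3 days and 16-27% on 6 days. The 35-day shift is largest at the lowest rate (7 − 2 = 5 to 15 − 7 = 8 points) and close to 0 at the highest rate with CV 0.

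**4. With a true effect.** Exact Poisson, as in step 2:
- B = 100, true reduction 60%, 50% response: 58.2% on 1 day, 95.8% on 35, 99.7% on 91.
- B = 100, true reduction 80%, 75% response: 49.0% on 1 day, 97.7% on 91.
- B = 8, true reduction 60%: 50% response is 89.2% on 1 day, 78.5% on 35 and 83.4% on 91; 75% response is 23.8% on 35 against 10.7% on 91.

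Mixed population (assumed median baseline 60 per 28 days, Poisson), 50%/75% response in percent:

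| Median true reduction | 1 day | 7 days | 35 days | 91 days |
|---|---|---|---|---|
| 20% | 39/28 | 27/8 | 23/4 | 23/4 |
| 60% | 64/48 | 63/30 | 64/24 | 64/23 |

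Across the mixed populations simulated, the average shift from 91 to 35 days is about 0-3 points for 50% response and 0-5 points for 75% response.

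**5. Seizure freedom.** If a fraction f of the subjects in an interval do not complete it, the reported rate is (1 − f) times the rate among completers. In interval 6, with completion read as 91 days, f = 1 and the rate is 0%. Elsewhere f is not given.

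**The case against.** The strongest reply is that the completion rule is deliberate. Core SAP 5.4.2 likewise requires completing the Core Study for seizure freedom, and it is the usual conservative handling of dropouts. That stands, and the rule should stay. The fault lies only in applying it to an interval that nobody can complete.

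The outputs are also descriptive: Extension SAP 5.2.2 and 5.2.3 plan no models and no p-values. That stands and limits the importance of the point. Derivation rules sit in separate programming specifications (Extension SAP 9), which may settle the interval denominator or suppress interval 6. That is possible, but the SAP as written does not do so. The one-day rule also resembles the Extension Full Analysis Set definition, which needs one seizure measurement; membership of a set is not the same as enough data to score a response.

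Three stronger readings are tempting.
- A reader might infer that truncation pushes 50% and 75% response up. It does so for non-responders and low-rate subjects, but step 4 shows the opposite where the true reduction exceeds the threshold at higher rates.
- A reader might expect late intervals to show rising response together with falling seizure freedom. No single scenario here shows both: with no effect, even the entry minimum gives 26 expected drop seizures in 91 days, so seizure freedom is near zero anyway.
- A reader might put a figure on how far seizure freedom is understated in other intervals. That needs f, and the assumption that non-completers would have been seizure-free as often as completers. The documents give neither.

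**Conclusion.** The concern holds in a limited form. One valid diary day can place a subject in a 13-week interval and score the subject for 50% and 75% response, while seizure freedom needs a completed interval. This rests on reading the garbled inclusion sentence as governing each interval.

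If completion means 13 weeks, and interval 6 is displayed, its seizure-freedom rate for perampanel-randomised subjects is 0% by construction. That part is schedule arithmetic and needs no model.

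For response rates, intervals of a few days are unreliable in both directions. The built-in 35-day interval distorts 50% response only modestly, by about 0-8 points with no effect under the assumed count model. The large one-day figures apply only to intervals that short, and neither their number nor the share truncated by early termination is given. No test or primary conclusion is touched. The text should still be corrected, because the display is the only view of efficacy over time and the correction is cheap.

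**What to change.** In Extension SAP 5.3.1:

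- Reword the inclusion sentence so that it clearly governs each 13-week interval.
- Require a minimum number of valid diary days in the interval for percent change and 50%/75% response: for example 28 days, or the 8 weeks that the Core SAP uses for short Maintenance data to obtain more stable estimates. At B = 8 with no effect, the chance of scoring as a 50% responder falls from 75.1% on 1 day to P(X ≤ 4 | mean 8) = 10.0% on 28 days or P(X ≤ 8 | mean 16) = 2.2% on 56 days. A 56-day minimum would leave no response data in the 35-day interval 6; a 28-day minimum would keep it.
- Define completion, including for a last visit held early within its window, and say whether the rule also governs 100% response.
- End the by-interval display at the last interval the schedule allows to be completed (five for Core-perampanel subjects, four for placebo switchers), or show later partial intervals without a seizure-freedom rate.
- Keep the completion requirement for seizure freedom and print the number completing each interval beside the rate.
- Do not restrict all response endpoints to interval completers: that conditions on staying on drug and drops subjects who leave for lack of effect.
- Keep all diary days in the overall-duration summary.

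The cost is a few sentences and one derivation flag. The downside is fewer subjects in the last displayed interval and the loss, from that interval, of subjects who stop very early in it.

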5.4 Pharmacokinetic, Pharmacodynamic, and PHARMACOGENOMIC/PHARMACOGENETIC ANALYSES

Not applicable.

5.5 SAFETY ANALYSES

All safety analyses will be performed on the Safety Analysis Set (Extension). Treatment-emergent adverse events will be summarized. The incidence of on treatment suicidality as measured by the C-SSRS will be summarized. Clinical laboratory parameters and vital signs data will be listed. Study Day 1 for all safety analyses is defined as the date of the first dose of perampanel.

5.5.1 Extent of Exposure

Total perampanel exposure will be calculated as the number of days between the date the subject received the first dose of perampanel (from Core Study or Extension Phase) and the date the subject received the last dose of study drug in Extension Phase (A or B).

The mean, modal, median, maximum and last daily dose over the conversion, extension maintenance (A+B), overall extension and overall perampanel treatment duration will be summarized.. The mean daily dose will be calculated by taking the average of all the doses taken weighted by the total duration of exposure and rounded to 1 decimal place.

5.5.2 Adverse Events

Adverse events will be addressed with respect to the Safety Analysis Set (Extension).

The AE verbatim descriptions (investigator terms from the CRF) will be classified into standardized medical terminology using the Medical Dictionary for Regulatory Activities (MedDRA). Adverse events will be coded to the MedDRA (Version 16.1 or higher) lower level term (LLT) closest to the verbatim term. The linked MedDRA preferred term (PT) and primary system organ class (SOC) will also be captured in the database.

A TEAE is defined as an AE that emerged during treatment, having been absent at pre-treatment (Baseline) or

- Re-emerged during treatment, having been present at pre-treatment (Baseline) but stopped before treatment, or

- Worsened in severity during treatment relative to the pre-treatment state, when the AE was continuous.

Only those AEs that are treatment emergent will be included in summary tables. All AEs, treatment emergent or otherwise, will be presented in subject data listings.

For subjects randomized to the perampanel treatment group in the Core Study, the first dose date of perampanel is from the Core Study. For subjects randomized to placebo in the Core study, the first dose date of perampanel is from the Extension Phase

TEAEs will be summarized. The incidence of TEAEs will be reported as the number (percentage) of subjects with TEAEs by PT and decreasing frequency. A subject will be counted only once within a PT, even if the subject experienced more than one TEAE within a specific PT. Treatment-related TEAEs will also be summarized.

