Extension A: During the Conversion Period, subjects who received perampanel during the Core Study will continue receiving perampanel in a blinded manner at the same dose last received during the Core Maintenance Period. Subjects who received placebo during the Core Study will begin treatment with perampanel in a blinded manner, following the same dosing regimen and titration schedule as that in the Core Study, starting at 2 mg/day and will then be up-titrated to the optimal dose, not to exceed 8 mg/day, per the investigator's discretion. After the double-blind Conversion Period, subjects can be titrated up to 12 mg/day (except in Japan, where the maximum allowed dose remains at 8 mg/day), at 2-week intervals per the investigator's discretion. During the Conversion and Maintenance Periods, all dose adjustments will be done via 1 dose level up or down. Those who cannot tolerate a minimum of 2 mg dose must discontinue from the study. (revised per Amendment 04)

Extension B: Perampanel dosing in Extension B will be the last dose the subject received at the end of Extension A. During the Treatment Period, all dose adjustments will be done via 1 dose level up or down. Those who cannot tolerate a minimum of 2 mg dose must discontinue from the study. (revised per Amendment 04):

Duration of Treatment (revised per Amendment 04)

Core Study:

- **Prerandomization Phase (Screening/Baseline):** 4 (minimum) to 8 weeks
- **Randomization Phase (Titration, Maintenance, Follow-up):** 18 weeks (6+12 weeks, respectively, for subjects continuing into Extension A) or 22 weeks (6+12+4 weeks, respectively, for subjects not entering into Extension A)

Extension A (Conversion, Maintenance, Follow-up): 52 weeks (6+46 weeks, respectively, for subjects continuing into Extension B) or 56 weeks (6+46+4 weeks, respectively, for subjects not entering into Extension B)

Extension B: Until perampanel is available commercially for the treatment of LGS, or accessible via EAP (if activated in the country in which a subject resides), unless the sponsor terminates the study or terminates the study in a particular country

Concomitant Drug/Therapy

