5.6.2 Adverse Events

The AE verbatim descriptions (investigator terms from the CRF) will be classified into standardized medical terminology using the Medical Dictionary for Regulatory Activities (MedDRA). Adverse events will be coded to the MedDRA (Version 24.1 or higher) lower level term (LLT) closest to the verbatim term. The linked MedDRA preferred term (PT) and primary system organ class (SOC) will also be captured in the database.

A TEAE is defined as an AE that emerged during treatment, having been absent at pre-treatment (Baseline) or

- Re-emerged during treatment, having been present at pre-treatment (Baseline) but stopped before treatment, or
- Worsened in severity during treatment relative to the pre-treatment state, when the AE was continuous.

Only those AEs that are treatment emergent will be included in summary tables. All AEs, treatment emergent or otherwise, will be presented in subject data listings.

TEAEs will be summarized by treatment group and by age group. The incidence of TEAEs will be reported as the number (percentage) of subjects with TEAEs by SOC and PT. A subject will be counted only once within a SOC and PT, even if the subject experienced more than one TEAE within a specific SOC and PT. The number (percentage) of subjects with TEAEs will also be summarized by maximum severity (mild, moderate, or severe).

The number (percentage) of subjects with TEAEs will also be summarized by relationship to study drug (related and not related). Summaries of treatment-related TEAEs will be produced.

There will also be summaries of TEAEs by dose at onset and exposure-adjusted event rates.

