8.2.2 Treatment Duration for Safety Analyses

For AEs, the perampanel treatment duration is considered to begin:

- at the first dose of perampanel in the Core Study and ends 28 days after the last dose of perampanel in Extension Phase A for subjects assigned to perampanel treatment during the Core Study
- at the date of first perampanel dose to 28 days after the last dose of perampanel in Extension Phase A for subjects assigned to placebo treatment during the Core Study.

The Post-treatment duration will begin on the day after the permpanel treatment duration during Extension Phase A.

AEs for the subject were collected and reported on the CRF starting from the time subject signed informed consent to the last visit in the Treatment Phase following subject's last dose. Serious AEs were collected for 28 days after the last dose.

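### Extension safety tables give only crude percentages of subjects, pooled over Core arms with unequal and truncated time at risk, so they reflect follow-up length as well as risk

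*SAP*

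**What the plan says.** Extension SAP 5.5.2 sets the measure for TEAEs: "The incidence of TEAEs will be reported as the number (percentage) of subjects with TEAEs by PT and decreasing frequency". Section 5.5.2.1 plans the number and percentage of subjects for serious events and for events leading to discontinuation. It also plans summaries of the special-interest groups without naming a measure. Neither section plans a rate per person-time, a time-to-first-event summary or a breakdown by time. Section 5.2.4 presents summaries by age group and overall, so the two Core arms share a column.

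Section 8.2.2 defines the adverse event window. For subjects randomized to perampanel it begins "at the first dose of perampanel in the Core Study and ends 28 days after the last dose of perampanel in Extension Phase A". In the Core-placebo arm it runs "at the date of first perampanel dose to 28 days after the last dose of perampanel in Extension Phase A". The same section says that adverse events were collected from consent "to the last visit in the Treatment Phase following" the last dose, with serious events collected for 28 days after it.

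Section 7 states: "Limited data summaries are being produced due to the early termination of the study". Section 5.5.1 derives total perampanel exposure to the last dose in Extension A or B and does not link it to adverse events. Section 5.3.1 splits efficacy into 13-week intervals.

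The Core SAP, section 5.6.2, goes further for its TEAEs: "There will also be summaries of TEAEs by dose at onset and exposure-adjusted event rates". Core SAP 5.6.2.2 adds exposure-adjusted rates for falls and for accident and injury events.

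**The concern.** A percentage of subjects with an event is easy to interpret when everyone is observed for a similar time. Here the plan makes time at risk unequal between the Core arms, pools them, and then applies the measure to a study that stopped early. A Core-placebo subject who stops soon after conversion counts in the denominator exactly as a Core-perampanel subject followed for more than a year.

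Protocol 9.1.3 gives the purpose of the Extension A treatment period: "The total treatment duration in Extension A is 52 weeks for evaluation of long term safety and efficacy". Percentages that depend on when the study stopped are a weak description of long-term safety. They are also hard to set beside the 18-week Core results or other long-term data. The sponsor plans exposure-adjusted rates in the Core, where planned treatment is equal, and not in the Extension, where it is not.

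**Working it through.** **1. Planned durations.** The Protocol synopsis gives Core treatment as "18 weeks (6+12 weeks, respectively, for subjects continuing into Extension A"; Protocol 9.1.3 gives Extension A as 52 weeks. With up to 8 weeks of prerandomization and 4 weeks of follow-up, 8 + 18 + 52 + 4 = 82 weeks. This reproduces the stated maximum of about 82 weeks on study (Protocol 9.1).

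**2. Range of the adverse event window.** Visit days come from Protocol Tables 5 and 8 (Day 1, Visit 7 on Day 127, Visit 14 on Day 491). The 28-day tail comes from Extension SAP 8.2.2.

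| Core arm | Longest | Shortest |
|---|---|---|
| Perampanel | (491 − 1)/7 = 70 weeks, plus 4 = 74 | (127 − 1)/7 = 18 weeks on drug, 22 with the tail |
| Placebo | (491 − 127)/7 = 52 weeks, plus 4 = 56 | days on drug; one dose gives 29/7 = 4.1 weeks with the tail |

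The perampanel minimum is about 18 weeks because Protocol Appendix 2 admits only subjects who completed Visit 7.

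**3. Effect on the percentage at a constant hazard.** The documents give no event rates, so these are assumptions. Crude % = 1 − exp(−h × w/52.18), with h per year and w in weeks.

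| h per year | 26 weeks | 56 weeks | 74 weeks | 74 vs 26 | 74 vs 56 |
|---|---|---|---|---|---|
| 0.05 | 2.46% | 5.22% | 6.85% | 2.8 | 1.3 |
| 0.5 | 22.05% | 41.53% | 50.79% | 2.3 | 1.2 |

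**4. Effect on a pooled column.** Assume equal arm sizes and 10% incidence per 18 weeks, so λ = −ln(0.9)/18 per week, or 30.5 per 100 subject-years. The stopping times are also assumptions.

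| Extension stops at | Windows (weeks) | Crude % by Core arm (perampanel, placebo) | Pooled crude % | First events per 100 subject-years |
|---|---|---|---|---|
| 52 weeks (all complete) | 74, 56 | 35.2, 27.9 | 31.6 | 30.5 |
| 26 weeks | 48, 30 | 24.5, 16.1 | 20.3 | 30.5 |
| 12 weeks | 34, 16 | 18.0, 8.9 | 13.5 | 30.5 |

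At a constant hazard, mean time to first event or censoring is p/λ, where p is the proportion with an event. The rate p/(p/λ) = λ is therefore free of follow-up length.

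**5. The same check with a front-loaded hazard.** Assume 20% incidence by 74 weeks, with 80% of the cumulative hazard H = −ln(0.8) in the first 6 weeks and the rest spread over the remaining 68. The rate is crude incidence divided by mean time at risk (the area under the event-free curve).

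| Window (weeks) | 22 | 56 | 74 |
|---|---|---|---|
| Crude % | 17.2 | 19.0 | 20.0 |
| First events per 100 subject-years | 47.8 | 21.3 | 17.1 |

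From 22 to 74 weeks the percentage changes 20.0/17.2 = 1.16-fold, while the rate changes 47.8/17.1 = 2.8-fold. At 4 weeks the percentage is 11.2%, so very short windows still matter.

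**The case against.** **The protocol.** Protocol Appendix 2 says Extension A safety analyses will be similar to those of the Core, so a reader might infer that the Extension SAP breaks that commitment. The documents do not support this. Appendix 2 points to Protocol 9.7.1.8, which itself plans only the number and percentage of subjects. Exposure-adjusted rates first appear in the Core SAP, so the difference is between two SAPs.

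**Limited reporting is disclosed.** Section 7 gives early termination as the reason for limited summaries, and laboratory and vital sign data are reduced to listings. That explains a short report. It does not make the retained percentages easier to interpret, since the same termination is what truncates follow-up.

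**No misleading contrast is tabulated.** There are no models or p-values, and the 74- against 56-week comparison between arms is never shown. This is fair, and it limits the harm to descriptive use. A pooled percentage still has no stated time base. Whether age groups differ in follow-up is unknown from the documents.

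**The rate has its own weakness.** This objection stands. Step 5 shows that for events concentrated in titration the rate moves more with follow-up than the percentage does. The documents do not say which hazard shape applies, so a rate alone is not enough.

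**The denominator is not already available.** This also stands. Exposure in 5.5.1 runs to the last dose in Extension A or B, whereas the adverse event window ends with Extension A.

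**Conclusion.** The concern holds in a limited form. The Extension percentages reflect follow-up length as well as risk. Under an assumed constant hazard of 0.05 to 0.5 per year the percentage differs about 2.3- to 2.8-fold between 26 and 74 weeks. Under the front-loaded assumption the difference between 22 and 74 weeks is only 1.16-fold. The actual size cannot be given, because the documents state neither event rates nor when the study stopped.

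Two stronger readings should be resisted. A reader might infer that follow-up length drives the percentages as much as risk does; nothing in the documents supports that balance, and it would be wrong for events confined to titration. A reader might also infer that time at risk runs from days to 74 weeks for everyone. Only Core-placebo subjects can have days on drug, and counted with the same 28-day tail as the 74 weeks, their minimum is about 4 weeks.

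This is a worthwhile, low-cost improvement to descriptive safety tables. No Core result, test or sample size is affected.

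**What to change.** In Extension SAP 5.5.2 and 5.5.2.1:

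- Beside each n (%), add subjects with a first event per 100 subject-years at risk, with total subject-years per column.
- Count person-time over the window of 8.2.2, from first perampanel dose to first event or the end of adverse event collection in Extension A. Do not use the exposure of 5.5.1. State the end date separately for serious and non-serious events, because 8.2.2 gives different collection periods.
- Show incidence by time since first perampanel dose, for example in the 13-week intervals already used for efficacy, with the number at risk in each interval.
- Show the main rows by Core arm as well as pooled. This matters most for events leading to discontinuation: Core-perampanel subjects entered the Extension only after completing the Core, so their first 18 weeks cannot contain such an event.

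The cost is SAP wording, one extra person-time derivation (including handling of partial onset dates) and wider tables. No new data are needed.
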